5.4 Heterogeneous Effects

We plan to conduct several heterogeneity tests that we believe are of central importance: respondent race, respondent political affiliation (within the white sample), prior beliefs about racial disparities and COVID-19, and the timing of participation vis a vis the events of Kenosha, WI.

We are very interested in studying how the impacts of our treatments vary by the race of the respondent. This is central to our research design. Specifically,

- Is the impact of racial concordance different by respondent race?
- Is the impact of a statement addressing racial injustice different by respondent race?
- Is the impact of information about racial disparities in the COVID-19 burden different by respondent race?

Moreover, within the white respondent population, we predict that there may be substantial heterogeneity by the respondent's political beliefs:

- Is the impact of racial concordance different for white republicans versus white democrats?
- Is the impact of a statement addressing racial injustice different for white republicans versus white democrats?
- Is the impact of information on racial disparities in disease burden different for white republicans versus white democrats?

We predict that the impacts of information on racial disparities in COVID burden should depend on individuals' prior beliefs:

- The information about RD should cause individuals who initially believed at baseline that there were small or non-existent racial disparities to update in the opposite direction of individuals who believed that the racial disparities were larger than they actually are.
- Thus, for all of our tests involving RD, we will interact the regressions with indicators for whether the priors were smaller or larger than the number we give in the videos.
- Moreover, there may be bigger impacts for individuals whose priors were less accurate, so we can also interact by the size of the gap between the information and the prior, separately for those with priors that were too low versus too high. This can also help us measure whether the information had an impact even for people with accurate priors, possibly through a salience effect.

We intend to compare the results of our hypothesis tests separately for the time period before the Jacob Blake police shooting in Kenosha, WI on August 23, 2020, and the time period after. We propose to do this for two reasons. First, we launched the study at a time when the large-scale protests from earlier in the summer following the murder of George Floyd had somewhat ebbed. So the events in Kenosha may bring issues of racial injustice to the fore. Second, and perhaps more importantly, polarization surrounding the narrative of the protests has markedly increased following the events of Kenosha. Several speakers at the Republican National Convention explicitly discussed the violent component of the protests, for example, and both candidates for the US presidency are making trips to Kenosha. This increased polarization is likely to have the most relevance for the white respondents in our study, and may enhance any differential response we find by political affiliation. We propose to split the sample into the period before August 23, 2020 and the period following August 26, 2020. We will omit surveys collected on days in the interim when Americans were only coming to learn about the events of Kenosha, WI.

We are also interested in secondary analysis exploring heterogeneity on the following categories of traits/characteristics:

- Age
- Level of baseline knowledge and health-preserving behaviors
- Place of residence (correlated with political affiliation, COVID-19 policies and phased reopenings, and socio-economic characteristics)

Given the many ways to cut the data for this secondary analysis, we will follow the methodology of Chernozhukov et al (2019) for this latter set of potential heterogeneous treatment effects.⁵

6. Robustness

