 - RD should have the largest impacts for individuals who have incorrect beliefs. Moreover, the impacts of the information should be different for individuals with priors about relative impacts on African Americans that are too low versus too high. (See Section 5.4, below).

4. Data Collection and Outcomes

We will run our experiment beginning on August 7, 2020. We are recruiting individuals that fit our screening criteria from an online survey firm. The data will be collected from respondent surveys. There is a short baseline module before individuals are exposed to the videos. Following the final video, there is an endline outcome module that all participants complete. Respondents also evaluate each video immediately after watching it. We also plan to follow up with individuals a few days after the treatment delivery for an additional survey to measure whether the videos changed behaviors. Prior to treatment, we ask all participants whether they would be willing to answer the follow-up survey. We allow individuals to enroll in the study, independent of their follow-up availability. We plan to control for willingness to answer a follow-up in all regressions. All of the survey responses will be downloaded in a .csv file for cleaning and analysis in R.

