5.3 Regression Analysis

We will perform different regression analyses to test the hypotheses listed above. Because our data contains many possible control variables, we will use a double-lasso procedure to select regression controls. We will also include a control for whether the participant's availability to participate in a

follow up survey (as indicted at baseline). These control variables are denoted as X in the regression specifications below.

Unless otherwise noted, we will examine treatment effects on knowledge of COVID symptoms, knowledge of COVID transmission, intended donation to a COVID-related charity, willingness to pay for masks, changes in reported behavior. In what follows, we present the minimal regressions to test each of the hypotheses, restricting to the smallest subset of treatments. However, we could also execute the same tests in the full sample, but with more treatment interactions.³

Note that the “COVID” indicator covers cases when doctors mention COVID plus racism, or COVID alone. In text, we refer to this group as the treatment group.

1. Baseline treatment effect: does any of the COVID-19 messaging affect knowledge, intended behavior, priorities in donation, or actual behavior?

- Question: does COVID messaging from doctors have any effect?

Samples: separate analysis for all respondents, black respondents, and white respondents.

Regression:

$$Y = \beta \cdot \text{COVID Video} + X'\gamma + \epsilon$$

2. Does racial concordance of the doctor in the COVID-19 video change the effectiveness for messaging?

- Question: Bolded, immediately above.

Samples: COVID video groups. Separate analysis for black and white respondents.

Regression:

$$Y = \beta \cdot \text{DocConcord} + X'\gamma + \epsilon$$

Alternate Specification: To allow, for a level effect of doctor concordance, we can also run the following modified regression, including both the COVID video and control groups.

$$Y = \beta \cdot \text{DocConcord} \cdot \text{COVID Video} + \alpha \cdot \text{COVID Video} + \delta \cdot \text{DocConcord} + X'\gamma + \epsilon$$

- Question: Bolded above, but using an alternate definition of concordance. We'll require a) all messengers or b) any messenger to concord with the respondent's race.

For any outcomes where β is of the same sign for white and black respondents, we will estimate the above equation again in the full sample.

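### No test or confidence interval is specified for whether effects changed around August 23; the race and party questions lack one too

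*Combined protocol and SAP*

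**What the plan says.** **Timing.** Section 5.4 says: "We intend to compare the results of our hypothesis tests separately for the time period" before the August 23 shooting and the period after it. It continues: "We propose to split the sample into the period before August 23, 2020 and the period following August 26, 2020". Surveys from the days between are omitted. No period-by-treatment term appears. Section 4 gives the start ("We will run our experiment beginning on August 7, 2020") but no end date, so the size of each period is unknown.

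**Race.** Section 5.4 asks "Is the impact of racial concordance different by respondent race" and puts parallel questions for the racial-injustice statement and the racial-disparity information. The models in Section 5.3 are fitted by race (for example, "Samples: COVID video groups. Separate analysis for black and white respondents") or pooled without a race interaction. The one rule that looks across races is for concordance: if the coefficient "is of the same sign for white and black respondents, we will estimate the above equation again in the full sample". That rule compares signs and does not test equality.

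**Party.** Section 5.4 asks "Is the impact of racial concordance different for white republicans versus white democrats", with two parallel questions. It gives neither a split nor an interaction.

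**Prior beliefs, for contrast.** Here an interaction is promised: "we will interact the regressions with indicators for whether the priors were smaller or larger" than the figure in the videos. For the secondary moderators (age, baseline knowledge and behaviour, residence) a published machine-learning method is named.

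**The concern.** Section 5.4 treats race, party, prior beliefs and timing as its central moderators. A claim that an effect changed after Kenosha, or differs between Black and white respondents, is a claim about a difference between two effects. It needs an estimate of that difference with its own standard error. Two separate tests do not supply one: a significant result in one part and a non-significant result in the other is common even when the true effects are equal, and splitting the sample makes it more common by lowering power in each part.

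Timing has a second weakness. Period is not randomised. If the people recruited online after August 26 differ from those recruited before August 23 in ways that modify the treatment effect, the change in composition will look like a response to the events.

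At stake are the claims of difference only. The pooled and race-specific treatment effects are not affected.

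**Working it through.** The plan states no alpha, power, effect size or period sizes for these comparisons, and the target of 20,000 (10,000 per race, Section 2.2) has no stated derivation. There is no figure of the plan's own to reproduce. The following assumes two-sided 0.05.

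**1. Chance of discordant results when the true effects are equal.** With independent subgroups of power p1 and p2,

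P(exactly one significant) = p1(1 − p2) + p2(1 − p1), which is 2p(1 − p) when the powers are equal.

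| Power in each subgroup | Exactly one significant |
|---|---|
| 5% (no effect in either) | 9.5% |
| 20% | 32% |
| 50% | 50% |
| 80% | 32% |
| 90% | 18% |
| 95% | 9.5% |

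A simulation with one million draws gave 9.5%, 50.0%, 32.0% and 18.0% at no effect, 50%, 80% and 90% power.

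**2. Splitting one sample by period.** Let λ be the noncentrality in the undivided sample: 1.96 + 0.84 = 2.80 for 80% power, and 1.96 + 1.28 = 3.24 for 90%. A period holding share f has noncentrality λ√f.

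| Undivided power | Split | Power in each part | Exactly one significant |
|---|---|---|---|
| 80% | 50:50 | 0.508, 0.508 | 50% |
| 80% | 30:70 | 0.335, 0.650 | 55% |
| 80% | 20:80 | 0.240, 0.707 | 61% |
| 90% | 50:50 | 0.630, 0.630 | 47% |
| 90% | 30:70 | 0.427, 0.774 | 54% |
| 90% | 20:80 | 0.305, 0.826 | 63% |

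For the 20:80 row at 80%: 0.240 × 0.293 + 0.707 × 0.760 = 0.070 + 0.537 = 0.61.

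**3. Direct test.** z = (b1 − b2)/√(se1² + se2²) rejects equal effects 5% of the time whatever the power (simulated 4.96% to 5.03%).

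**4. Precision of the direct test.** If se is the standard error of the pooled effect, the difference has standard error se × √(1/f + 1/(1 − f)). That is 2 se at 50:50 and √(1.25 + 5) = 2.5 se at 20:80.

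**5. Composition.** Suppose the events change nothing, a baseline trait X raises the treatment effect by 0.5, and the prevalence of X moves from 30% before to 70% after. The apparent change is 0.5 × (0.70 − 0.30) = 0.20. Adjusting outcome levels for X within period leaves it at 0.20. Adding a treatment-by-X term brings it to 0.00 (checked by simulation).

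**6. Concordance by race.** Assume two doctor races. Let R = 1 for a Black respondent, C = 1 for a concordant doctor and D = 1 for a Black doctor. Then D = 1 − R − C + 2CR. The concordance effect is the doctor-race effect δB among Black respondents and −δW among white respondents, so the difference by race is δB − (−δW) = δB + δW. D is fixed by the video. Once the video fixed effects of Section 6.1 enter alongside R and C, the product CR is no longer identified.

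**The case against.** The strongest reply is that the plan nowhere adopts the faulty rule. A reader might infer from Section 5.4 that a difference will be declared when one period is significant and the other is not. No sentence says so. Comparing results could mean comparing estimates and intervals, and Section 5.4 describes all four moderators as heterogeneity tests. This stands, so the rates above are conditional on how the comparison is read. They also depend on the assumed power; halving an 80%-powered sample is a natural model for the period split but not for race, where each group has its own target of 10,000.

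A reader might also infer that interactions were rejected for race and party because one is promised for prior beliefs. That does not follow. Section 5.3 describes its equations as the minimal ones, and Section 5.4 writes out no equation for any moderator. For race the test is missing but not excluded; for party there is no method at all.

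Next, a model with treatment and all controls interacted with the subgroup reproduces the difference between the two separate coefficients, so the interval could be obtained from output already planned. That holds if both parts use the same controls. Double-lasso selection (Section 5.3) run within each part might choose different ones. What is missing is the commitment to report the contrast.

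Finally, a reader might suspect that the period comparison was passed off as planned before launch. The documents do not support this: the draft is dated September 4, Section 4 gives an August 7 start, and Section 5.4 itself describes the launch and the later events.

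**Conclusion.** The concern holds as a gap in specification. It is explicit for timing, where the stated method is a split sample and a comparison of tests with no estimate of the difference. It holds by omission for race, where the questions are about differences but no written model contains one. For party the plan is silent, and calling that a choice of separate tests would go beyond the text.

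If differences are read from significance in each part, equal effects would appear discordant about 10% to 60% of the time over the powers and splits examined, against 5% for a direct test. This rests on two-sided 0.05 and assumed power and period shares. The range is not a bound: at 99% power in both parts the rate is 2 × 0.99 × 0.01 = 2%, and a split more lopsided than 20:80 could exceed the upper figure. If estimates and intervals are compared directly, these rates do not apply, but the plan does not commit to that. The correction should be made before claims of difference are reported.

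**What to change.** **Timing.** With the interim days omitted and G marking the later period, fit one model:

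Y = b·T + d·T·G + p·G + X′g + (X·G)′h + (T·X)′k + e

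Use one set of controls for both periods. Report d with its confidence interval as the sole basis for any claim of change, and label the split-sample results descriptive. The T·X terms are needed because X·G alone adjusts outcome levels and leaves composition-driven differences in effect. Measured covariates cannot remove all such differences, so describe what remains as an association with period.

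**Race and party.** Do the same with treatment-by-race for the AMA statement and the racial-disparity information, and with treatment-by-party within the white sample. Neither moderator is randomised, so the same caution on wording applies.

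**Concordance by race.** Report the difference with its interval. State that it equals the sum of the doctor-race effects across the two respondent groups, cannot be separated from chance differences between videos, and is not identified when video fixed effects are included.

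**Cost.** A few regressions and a paragraph of plan text, with no new data. The downside is precision: the interval for a difference is 2 to 2.5 times as wide as that for the pooled effect at splits from 50:50 to 20:80, so fewer claims of difference will be supported.

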2.2 Recruitment and Sampling

We are using Lucid to recruit a sample and to compensate subjects for their participation. Our total target sample size is 20,000 subjects, 10,000 African American respondents, and 10,000 White American respondents. We require all participants to be age 18 or older, and we are targeting individuals who have *not* completed a college degree.

Figure 1: Treatment Design

Note: There are 5 randomization instances summarized in this diagram. For the fully extended tree with all 24 final individual cells, see Figure 2.

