5.1 Balance Checks

We will conduct a series of balance tests across treatment arms to ensure that there are no chance differences between subjects in the various arms. We will regress characteristics measured pre-treatment on indicators for the arms and test their individual and joint significance. Balance tests will be conducted using all of the variables measured in the baseline survey.

We will also test for balance in attrition rates (see Section 6.2, below).

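### The before/after Kenosha comparison of treatment effects is observational, and no planned step removes a change in respondent mix between the two periods

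*Combined protocol and SAP*

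**What the plan says.** Section 5.4 introduces its first group of subgroup questions with "We plan to conduct several heterogeneity tests that we believe are of central importance", and timing relative to the Kenosha events is one of them. The hypothesis tests are to be run separately in each period and compared: "We propose to split the sample into the period before August 23, 2020 and the period following August 26, 2020". The days between are dropped: "We will omit surveys collected on days in the interim when Americans were only coming to learn about the events of Kenosha, WI". Two reasons are given, renewed attention to racial injustice and greater polarization, and the plan adds: "This increased polarization is likely to have the most relevance for the white respondents in our study".

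Four other places bear on whether the periods are comparable:

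- **Recruitment (Section 2.2).** "Our total target sample size is 20,000 subjects, 10,000 African American respondents, and 10,000 White American respondents". These are overall totals, with none per period.
- **Randomization (Section 2.3).** Within race, treatment is stratified on age, gender and region.
- **Balance (Section 5.1).** "We will conduct a series of balance tests across treatment arms". Calendar periods are not mentioned.
- **Adjustment (Section 5.3).** Controls chosen by double lasso, plus willingness to be followed up, enter every regression as the additive term X′γ.

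Section 6 discusses differences between videos and attrition, but not comparability of the two periods.

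**The concern.** Randomization makes the arms comparable within each period. It does not make the people surveyed before August 23 comparable with those surveyed after August 26. Respondents come from an online panel, and nothing in the plan fixes the mix of age, region or party from one period to the next.

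Mix matters because the plan itself expects effects to vary: by race, by party among white respondents, and by prior belief for the racial-disparity message. When effects vary between groups, the average effect in a period depends on the group shares in that period. A change in shares can then produce an apparent before/after change, or hide a real one, in a comparison that the plan ranks as central.

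Political affiliation raises a further difficulty. It is collected in the baseline module of the same session, so for later respondents it is measured after the events and may itself have moved.

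**Working it through.** The documents give no power, alpha, effect size, SD or count per period, so there is no figure of the plan's own to reproduce. What follows is an illustration under stated assumptions.

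**Step 1: why additive controls do not help.** Let a baseline group W have share p, and let its treatment effect exceed that of the others by g. The average effect in a period is τ + g·p. With no event effect,

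spurious change = (p_after − p_before) × g.

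An additive term in W shifts outcome levels. It leaves the treatment coefficient averaging over whatever mix is present.

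**Step 2: inputs.**

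- From the plan: 20,000 respondents, 10,000 per race (Section 2.2); start on August 7 (Section 4: "We will run our experiment beginning on August 7, 2020"), which gives 16 days, August 7–22, before the split.
- Assumed: two-sided 0.05; SD 1; even split between periods; 1:1 comparison within the COVID-video group; two-thirds of respondents allocated to COVID videos. The allocation figure is not shown. Two-thirds agrees with the 24 cells stated under Figure 1 if these are 2 × 2 × 2 × 3 equal cells.
- Ignored: the loss of the omitted interim days.

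**Step 3: standard error of the before/after difference in effects.** With n respondents per period, SE = √(2 × 4/n).

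- Pooled, COVID-video group: 20,000 × 2/3 = 13,333, so n = 6,667 and SE = √(8/6,667) = 0.035.
- White sample, COVID-video group: 10,000 × 2/3 = 6,667, so n = 3,333 and SE = √(8/3,333) = 0.049.

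**Step 4: false-positive rate.** For a spurious shift b, the rate is Φ(−1.96 + b/SE) + Φ(−1.96 − b/SE).

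| Sample | Assumed mix change × effect gap | b (SD) | Rate |
|---|---|---|---|
| Pooled | shift set directly | 0.01 | 6% |
| Pooled | 20 points of race share × 0.15 | 0.03 | 14% |
| Pooled | shift set directly | 0.06 | 41% |
| White | 10 points of party share × 0.15 | 0.015 | 6% |
| White | 20 points of party share × 0.15 | 0.03 | 9% |

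**Step 5: simulation.** There were 600 runs per scenario, with 1:1 arms, robust SEs and no true event effect. The group's main effect was allowed to differ by period, as separate regressions with X′γ would allow.

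| Mix change × gap | Rate, 5,000 per period | Rate, 10,000 per period |
|---|---|---|
| none | 5.5% | 5.3% |
| 10 points × 0.10 SD | 7.2% | 7.8% |
| 20 points × 0.20 SD | 17.3% | 26.7% |
| 30 points × 0.40 SD | 84.2% | 98.5% |

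At 20 points × 0.20 SD and 5,000 per period, the mean spurious change was 0.0404 SD both with and without the main-effect control. After a treatment-by-group term was added, the mean spurious change was about zero in every scenario (−0.0007 to 0.0005 SD) and the rejection rate was 4–7%.

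**Step 6: scale.** The before/after difference detectable with 80% power is (1.96 + 0.84) × √(8/5,000) ≈ 0.11 SD in one full race sample, and (1.96 + 0.84) × √(8/10,000) ≈ 0.08 SD in all 20,000. Modest mix changes produce shifts well below these.

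**The case against.** The strongest reply is that much of this is already handled. Most hypotheses are tested separately by race, and a change in race mix cannot affect a white-only or Black-only comparison. Tests of the racial-disparity message are interacted with prior beliefs. The plan's interest in the events centers on white respondents by political affiliation, and a comparison made within party is not moved by a change in party shares. Every regression carries controls.

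Most of this stands, and it narrows the point. It would be wrong to say that nothing adjusts. What remains is that additive controls do not address effect-modifier mix, that several tests also pool all respondents (Hypotheses 1 and 5, the AMA main effect in Section 5.3, and Hypothesis 2 when signs agree), and that age, region and education mix within race is left open.

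A reader might also infer that the plan credits any change to Kenosha. The text does not support that: it states a comparison and a rationale, in conditional language. Nor do the documents support the inference that the two periods did recruit different mixes, since no mix by period is given.

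A last objection is that adjusting for party, if the events moved party reporting, could remove part of a real change. That is correct, and it is why party belongs in a sensitivity analysis rather than the main adjustment.

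**Conclusion.** The point holds in limited form. The cross-period difference in effects is observational, and no planned step removes a change in effect-modifier mix from it. The treatment effect estimated within each period is not in question.

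Under the stated assumptions the distortion is slight for modest shifts: about 6% against a nominal 5% for 0.015 SD in whites. It is moderate for 0.03 SD, at about 9% in whites and 14% in pooled tests within the COVID-video group. It takes a large change in the share of a strong modifier to produce a finding by itself. The mix changes, effect gaps, period sizes and allocation are all assumptions. The 14% must not be carried over to the race-specific tests, where race mix plays no part and the standard error is larger.

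The correction is worth making because the comparison is ranked as central and the remedy is cheap.

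**What to change.** 1. Extend the Section 5.1 balance table to before versus after, within race.
2. Estimate the contrast in one model per race sample, with treatment-by-period plus treatment-by-age, gender, region and education. Alternatively, reweight both periods to a common mix on these variables. For tests that pool all respondents, add treatment-by-race.
3. Report the distribution of political affiliation by period, and show results with and without treatment-by-party terms as a sensitivity analysis.
4. Describe the result as a before/after difference between recruitment periods, not as an effect of the events. Steps 2 and 3 deal only with measured characteristics; unmeasured mix and other changes over calendar time remain.

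Repeating the contrast at placebo cut dates within August 7–22 is optional; a 16-day window gives it little power.

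The cost is a change of wording, a few extra regressions on baseline variables the survey already collects, and slightly wider intervals for the period difference.
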